8.1.5. Reporting of Serious Adverse Events

The Investigator will review each SAE and evaluate the severity and the causal relationship of the event to study drug. Serious AEs that occur after the last study visit and come to the attention of the Investigator must be reported only if there is (in the opinion of the Investigator) reasonable causal relationship with the study drug. Serious AE reporting contact information is provided in [Table 1](#).

The Investigator is responsible for providing notification to the Sponsor ([Table 1](#)) of any SAE, within 24 hours of when he or she became aware of the event, whether deemed study drug related or not.

An SAE report form template will be provided to the Investigator by the Sponsor (or designee) prior to study initiation, with the preferred format for reporting SAEs.

As a minimum requirement, the initial notification should include the following information:

- Study number
- Subject number
- Name of Investigator
- AE term
- Criterion for classification as ‘serious’
- Study drug name
- Causality assessment (if sufficient information is available to make this classification)
- Identifiable reporter of event

If clarification is requested by the Sponsor for omitted or discrepant information in the initial notification, the Investigator or an authorized delegate is responsible for sending the requested information within 24 hours.

Initial reports of SAEs must be followed later with detailed descriptions, including clear copies of other documents as necessary (e.g., hospital reports, consultant reports, autopsy reports), with the study subject’s personal identifiers removed. Additional information on the SAE may be requested, which the Investigator or an authorized delegate must send to the SAE reporting contact ([Table 1](#)).

The Sponsor is responsible for expedited reporting of qualifying events to relevant regulatory authorities. It is the Investigator’s responsibility to notify the IRB of all SAEs that occur at his or her site. Investigators will also be notified by the Sponsor of all unexpected, serious, drug-related events [Investigational New Drug (IND) safety reports; also known as SUSARs] that occur during the clinical trial from any other studies or study sites. The Investigator is responsible for notifying its IRB of these events.

8.1.6. Other Reportable Events

Certain events that occur in the absence of an AE should be reported to the Sponsor. These include the following events:

- Pregnancy Exposure (subject or subject's partner becomes pregnant at any time during study participation and through 30 days post-dose).
 - Should a female subject or partner of a male subject become pregnant during the study, the subject will inform the Investigator.
 - The subject will be asked to follow up with the study site to report the eventual outcome of the pregnancy. The information will be tracked by the Sponsor.
 - The outcome of all pregnancies (spontaneous miscarriage, elective termination, normal birth or congenital abnormality) must be followed up and documented even if the subject was discontinued from the study.
 - Pregnancy in itself is not regarded as an AE.
 - All reports of congenital abnormalities/birth defects are SAEs. Spontaneous miscarriages should also be reported and handled as SAEs. Elective abortions without complications should not be handled as AEs.
- Lactation Exposure (subject was taking study drug while nursing an infant).
- Accidental Exposure (someone other than the study subject was exposed to study drug).
- Overdose of Study Drug (defined as dosing > 4 capsules in a 24-hour period) as a result of a dosing amount error should be reported. Any adverse outcomes of the overdose should be recorded as AEs/SAEs according to the procedures described in Section 8.1 through Section 8.1.5. Intentional overdose of study drug should be evaluated as a potential AE/SAE and reported accordingly.
- Other medication errors that potentially place subjects at greater risk of harm than was previously known or recognized (i.e., study drug was administered via an incorrect route).

9. STATISTICS

Following are proposed statistical analyses. A separate Statistical Analysis Plan (SAP) will be generated and finalized prior to analysis. The SAP will specify the details of all statistical analyses, including all efficacy and safety analyses to be performed.

9.1. Determination of Sample Size

Recent studies of MDD using change from Baseline in MADRS total scores suggest that placebo will yield an approximately nine unit decrease over four weeks with a SD of around 9.2. SP-624 is expected to yield at least a 12 unit decrease in MADRS total score over four weeks with a similar SD of around 9.2. A minimum of 150 subjects per treatment arm (300 total) would be needed to detect a treatment difference of three units with 80% statistical power. The sample size was estimated using NQuery 8 (V8.5.2.0) two group test of equal means (MTT0-1: www.statsols.com).

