5. SELECTION AND WITHDRAWAL OF SUBJECTS

5.1. Subject Recruitment, Enrollment, and Identification

Subject recruitment and enrollment will be organized and overseen by the Investigator at the site following approval of the study protocol, ICF, and any study specific advertisements/recruitment materials by the respective IRB.

Subjects will be recruited via advertisements, physician referral, and from databases kept by the research center.

A sufficient number of subjects will be screened in order to ensure that a total of approximately 300 subjects who satisfy the entry criteria are randomized to treatment.

Each subject's signed and dated ICF to participate in the study must be obtained before conducting any study-related procedures. All subjects who sign an ICF will be given a unique Screening identification number and their study status will be tracked on a study Screening and Enrollment log maintained in the Investigator study files.

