7.2.4. Assessment of Efficacy

Efficacy assessments will be conducted by individuals with sufficient experience conducting the below rating scales who have received centralized rater training and have been approved by the PI and Sponsor. Whenever possible, the same rater should assess the same subject throughout the study.

The schedule of these safety assessments is provided in the SOE ([Table 2](#)), and the study-specific procedures for completion of these assessments are detailed below.

Assessments should not be performed on subjects who have missed two or more consecutive study drug doses immediately before the Week 1, Week 2, Week 3, or Week 4 / Premature Discontinuation visits.

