9.3.4.1. Primary Efficacy Endpoint Analysis

The MADRS is a 10-item scale whose total score can range from 0 to 60. The primary efficacy variable is change from Baseline in MADRS total score at Week 4, for testing superiority of SP-624 vs. placebo in adults with major depressive disorder. The analysis will be completed using observed data without imputation. Scores will be taken at 4 weeks regardless of subject discontinuation from treatment. Subjects will not be treated with any other antidepressant medication until at least the completion of the Week 5 visit.

The change from Baseline in MADRS total score at Week 4 will be analyzed from the difference in least square mean change using MMRM, with change from Baseline in MADRS total score at each visit as the response variable. The MMRM model will include age, weight, and baseline

MADRS total score as covariates, with factors for treatment, visit (Weeks 1, 2, 3, and 4; as a categorical variable), treatment by visit interaction term, gender, and site as a fixed effect. An unstructured covariance matrix will be used for the within-subject correlation. Kenward-Rogers approximation will be used to calculate the denominator degrees of freedom. The primary efficacy endpoint will be calculated using an estimate statement. Subjects from low enrolling sites may be pooled in order to help with model convergence.

In the event of a model which fails to converge, additional strategies to address convergence may be required such as alternative covariance structures, using a maximum likelihood versus restricted maximum likelihood (REML) estimation, or dropping variables.

The protocol may include approximately 40 sites and sites with less than 10 subjects will be pooled to obtain at least 10 subjects. Sites would be pooled in order of the site number and, if necessary, the last un-pooled site will be pooled with the last set of sites pooled.

Additional variables of interest that may be evaluated as covariates will be identified in the SAP, such as age of onset of depression and number of lifetime episodes.

Additionally, results from the primary outcome will be summarized for the PP population.

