9.3.5. Sensitivity Analyses

A dropout rate of 20-30% is typically seen in MDD studies. The mechanisms that cause missing data may be missing at random (MAR) or may be missing not at random (MNAR). The MMRM model (especially as implemented within the PROC MIXED procedure in SAS) used in the primary analysis of the primary efficacy endpoint relies on the assumption of MAR. Hence, a sensitivity analysis for the primary endpoint and secondary endpoints will be performed using a pattern-mixture modeling approach (Kenward, et al 2003).

Additionally, subjects will be grouped by the visit at which they had their last MADRS total score measured. This will result in five categories of discontinuation: Week 1 dropouts, Week 2 dropouts, Week 3 dropouts, Week 4 dropouts, and completers. Mean change from Baseline in MADRS total score will be plotted by the dropout category and by reason for discontinuation, in order to assess whether this efficacy measure appears to be correlated with study dropout.

If missing data are greater than 25% or the pattern-mixture model provides a different interpretation of the treatment comparison for the primary endpoint, a multiple imputation analysis may also be performed using a fully conditional specification (FCS) approach using variables identified in the SAP.

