# 5 Sample Size Justification

Recent studies of MDD using change from Baseline in MADRS total scores suggest that placebo will yield an approximately nine unit decrease over four weeks with a standard deviation (SD) of around 9.2. SP-624 is expected to yield at least a 12 unit decrease in MADRS total score over four weeks with a

Form STAT401.V3 Page 5 of 23

Client/Project	Arrivo/Sirtsei 201
Version and Date	V01 August 26, 2022

similar SD of around 9.2. A minimum of 150 subjects per treatment arm (300 total) would be needed to detect a treatment difference of three units with 80% statistical power. The sample size was estimated using NQuery 8 (V8.5.2.0) two group test of equal means (MTT0-1: www.statsols.com).

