#### **8.1.1** Efficacy Assessment Windowing

For all efficacy analyses, windowing will be applied to ensure study day of assessment does not fall too far from scheduled assessment day. Assessments will be considered part of the scheduled visit window if they fall within  $\pm$ 3 days of the nominal study visit day. In the event of multiple assessments within the same visit window, the assessment closest to the nominal study day will be used. In the event of a tie, the

Form STAT401.V3 Page 9 of 23

Client/Project	Arrivo/Sirtsei 201
Version and Date	V01 August 26, 2022

earliest study day will be used. A visit must be completed within 2 days of last treatment dose to be included as a treatment period visit. Visits completed 3 or more days after last dose will be excluded from the treatment period analysis. Follow-up period windowing will be relative to date of last dose of study drug: assessments completed 3 to 10 days after the last dose of study drug will be windowed to the Week 5/1-Week Follow-up Visit.

Efficacy assessment listings will include both the reported and windowed visit labels. Any assessment completed outside of the windows for which that particular assessment was scheduled to be completed per the protocol will be labeled as "Out of Window".

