**Table 8.1, Handling of Intercurrent Events** 

Estimand	Intercurrent Event	Rule / Rationale
Primary	Premature discontinuation /	Hypothetical "as own treatment" strategy. Clinical
	Permanent treatment	course is the same as other subjects in the same
	discontinuation	treatment group, who had not discontinued study
		treatment.
		Exclude observations that occur more than 3 days
		after the last dose of study drug for subjects who
		discontinue. The objective of the study is to
		evaluate the effect of SP-624 subjects who are
		provided drug to take on a standard schedule up to 4
		weeks. After 3 days, the drug should be cleared
		from all subjects, so the inclusion of any such data
		point is inconsistent with the goal of the estimand.
	Drug non-compliance / Missed	Treatment policy strategy.
	study medication	Some degree of non-compliance missed doses
		would be expected to occur in standard use.
	Protocol deviations not leading	Treatment policy strategy
	to study discontinuation	Overall, if not sufficient to lead to subject removal,
		the expectation is that they would not significantly
		impact subject results.
	Concomitant medications in	Treatment policy strategy
	violation of the protocol	This is expected to be a rare event in this clinical
		trial and treatment effect will be estimated
		irrespective of concomitant medication violations.

The hypothetical "as own treatment" strategy was selected for premature discontinuation or treatment discontinuation intercurrent events to evaluate the effect of treatment with respect to its pharmacologic efficacy. For the change from week 4 to week 5 follow-up secondary analysis, only subjects that were included in the week 4 primary analysis will be used. This should provide the most unbiased data for this

Form STAT401.V3 Page 12 of 23

Client/Project	Arrivo/Sirtsei 201
Version and Date	V01 August 26, 2022

phase 2 study to inform future studies. The treatment policy strategy will be used for all other defined intercurrent events.

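### The 80% power holds only if virtually every randomised subject gives a usable Week 4 MADRS score; no allowance is made for loss.

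*Protocol*

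**What the plan says.** The sample size is justified in three places: the protocol synopsis, Protocol 9.1 and SAP 5. All take a placebo decrease of about 9 points, a decrease of at least 12 on SP-624 and an SD of around 9.2 in both arms, and use a two-group test of equal means. Protocol 9.1 concludes "150 subjects per treatment arm (300 total) would be needed to detect a treatment difference of three units with 80% statistical power". SAP 5 repeats it: "A minimum of 150 subjects per treatment arm (300 total) would be needed to [...]". None mentions dropout, evaluable subjects or an inflation step.

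The same number is the recruitment target. Protocol 5.1 plans that "a total of approximately 300 subjects who satisfy the entry criteria are randomized to treatment".

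On loss, Protocol 9.3.5 states "A dropout rate of 20-30% is typically seen in MDD studies", and SAP 8.3.5.5 says the same. On which Week 4 scores count, the documents pull in different directions:

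- Protocol 9.3.4.1: "Scores will be taken at 4 weeks regardless of subject discontinuation from treatment".
- Protocol 7.2.4: "Assessments should not be performed on subjects who have missed two or more consecutive study drug doses immediately before the [...]" Week 1 to Week 4 visits.
- SAP 8.1.1: "Visits completed 3 or more days after last dose will be excluded from the treatment period analysis".
- SAP Table 8.1, for subjects who discontinue: "Exclude observations that occur more than 3 days [...]" after the last dose.

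The primary analysis (Protocol 9.3.4.1, SAP 8.3.5.4) is an MMRM on change from baseline with baseline MADRS as a covariate. The protocol specifies observed data without imputation.

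**The concern.** A two-group test of means counts subjects who have the outcome. If the number it returns is also the number randomised, the stated power assumes almost no missing outcomes. Both documents say that trials in this condition typically lose a fifth to a third of subjects or slightly less (20-30%), yet the power statement takes no account of it.

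Protocol 2.3 makes further studies depend on what this trial shows. Someone reading a negative result would take the chance of missing a true 3-point effect to be 20%. If that figure holds only with complete Week 4 data, or only because of a gain from the analysis model that is never stated, the reader needs to know.

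**Working it through.** **Inputs.** Difference δ = 3 and SD σ = 9.2 (Protocol 9.1); two-sided α = 0.05 (Protocol 9.3.1, SAP 8.1); about 150 randomised per arm (Protocol 4.4 and 5.1).

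**Step 1: reproduce the stated figure.** With n analysable per arm, T follows a noncentral t distribution with 2n − 2 degrees of freedom and noncentrality δ / (σ√(2/n)). Power is the probability that |T| exceeds the two-sided 5% critical value.

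- n = 150: 3 / (9.2 × √(2/150)) = 2.824, critical value 1.968, power 80.4%
- n = 149: noncentrality 2.815, power 80.1%
- n = 148: noncentrality 2.805, power 79.8%

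So 149 per arm are needed and 150 reproduces the plan's figure. It contains no hidden allowance: if 150 already included 20% loss, the evaluable number would be 150 × 0.8 = 120, which gives 71.1%, not 80%.

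**Step 2: does a subject who stops drug still give a Week 4 score?** Protocol 9.3.4.1 suggests so. But Protocol 7.2.4 says the assessment should not be done after two or more consecutive missed doses just before the visit. If it is done anyway, SAP 8.1.1 drops it at 3 or more days after the last dose, and Table 8.1 at more than 3 days. On either cut-off, a subject who stops some days before Week 4 has no usable score. An early discontinuation visit does not fill the gap, because SAP 8.1.1 assigns efficacy visits by actual day, within 3 days of nominal.

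**Step 3: power of the stated test with scores missing.** Put n = 150 × (1 − d):

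| Missing d | n per arm | Noncentrality | Power | Difference detectable with 80% power |
|---|---|---|---|---|
| 5% | 142.5 | 2.753 | 78.3% | |
| 10% | 135 | 2.679 | 76.1% | |
| 15% | 127.5 | 2.604 | 73.7% | |
| 20% | 120 | 2.526 | 71.1% | 3.34 |
| 25% | 112.5 | 2.446 | 68.3% | 3.45 |
| 30% | 105 | 2.363 | 65.2% | 3.57 |

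**Step 4: what the planned MMRM recovers.** The documents give no correlations and no SDs before Week 4, so these are assumptions: SDs of change 5.5, 7.2, 8.4 and 9.2 at Weeks 1-4; between-visit correlation 0.5-0.8, AR(1) or compound symmetry; dropouts' last scores spread evenly over Weeks 1-3; correlation r of baseline with change equal at every visit. For each dropout pattern, invert the covariance block of the visits observed; sum these over patterns weighted by subject numbers; invert the sum. The Week 4 element V is the variance of an arm mean, and the noncentrality is 3/√(2V), with completer degrees of freedom.

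One case: 20% dropout, compound symmetry 0.6, no baseline adjustment gives V = 0.643, so the noncentrality is 3/√1.287 = 2.645 and power is 75.0%. Baseline adjustment subtracts r²σⱼσₖ from each covariance. Ranges over all the correlation settings:

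| Baseline-change correlation | 20% dropout | 30% dropout |
|---|---|---|
| No adjustment | 72-77% | 67-75% |
| 0.3 | 76-81% | 71-79% |
| 0.5 | 83-87% | 78.5-85% |

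The value of r at which power is exactly 80% is 0.26-0.43 at 20% dropout, 0.30-0.48 at 25% and 0.35-0.53 at 30%. If a quarter of dropouts have no post-baseline score at all, it is 0.31-0.43 at 20% and 0.40-0.53 at 30%.

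**The case against.** The strongest reply is that nothing is miscalculated and that the 65-71% describes an analysis nobody will run. The primary MMRM keeps dropouts' earlier visits and adjusts for baseline, and with a baseline-change correlation of 0.5 it exceeds 80% at 20% dropout and roughly reaches it at 30%. This stands: 65-71% is a lower bound at the stated SD, and the trial is not shown to be underpowered. It does not rescue the power statement, which names a test with no covariate, gives no correlation and claims no such gain.

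The 20-30% is a typical rate for MDD studies of unstated length, not a forecast for a 4-week trial. That also stands. At 10% dropout the same MMRM with r = 0.3 gives 80-83%. Even so, the stated test is already at 78.3% with 5% missing.

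The inputs are rounded. At 150 per arm, an SD of 9.0 gives 82% and 9.5 gives 78%, so the one-subject margin means little in itself. The 12-point decrease is worded as a minimum, so true differences of 3.34-3.57 are not outside the sponsor's expectation. The source of the 9.2 is not named, so how far it already reflects loss or adjustment cannot be known. These points limit the precision of the figures, but none supplies an allowance for loss.

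Two further defences fail. SAP 8.3.5.3 writes a one-sided alternative, and one-sided 0.05 would need only 117 per arm; but both documents test two-sided, and 117 does not reproduce 150. Calling 150 a minimum adds no headroom when planned enrolment is about 150 per arm.

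Finally, the SAP is dated August 2022, after the planned last visit in November 2021, and a negative result should be read mainly from its confidence interval. That argues against touching enrolment, not against stating the assumption.

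**Conclusion.** The concern holds. The 150 per arm is a correct number of analysable subjects presented, without saying so, as the number to randomise. For the stated test, losing more than one Week 4 score per arm takes power below 80%. At the dropout both documents call typical, power is 71-65% and the implied 20% false-negative risk becomes 29-35%.

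Those figures rest only on the documents' own inputs, taking dropout to mean a missing Week 4 score. Whether the planned analysis reaches 80% is open. Under the assumptions in the check it runs from 67% to 87% for 20-30% dropout, depending mainly on a baseline-change correlation that the documents do not give.

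**What to change.** Add to the synopsis, Protocol 9.1 and SAP 5:

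> This calculation assumes a Week 4 MADRS score from all 150 subjects per arm; no allowance is made for missing scores. For the two-group test stated (difference 3, SD 9.2, two-sided 0.05), power is 71%, 68% and 65% if 20%, 25% and 30% of Week 4 scores are missing.

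Follow it with a short table giving the power of the baseline-adjusted MMRM over stated values for dropout, between-visit correlation and baseline-change correlation, with the source of each value or a note that it is assumed.

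The cost is one paragraph and one small table in three places, and a less favourable figure for the two-group test. Enrolment and the analysis stay as they are.

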9.2. Analysis Populations

Within each population, analyses will be performed comparing subjects and by-treatment assignment (SP-624 vs placebo).

- All Subjects Population – all subjects who sign informed consent and are assigned a unique subject identification number. This population will be used to summarize disposition.
- Modified Intent-to-Treat (mITT) Population – all subjects who are randomized to receive treatment, receive at least one dose of study drug, and have a Baseline and at least one post-dose efficacy assessment. This population will be the primary population used to summarize demographics, baseline characteristics, medical history, treatment history, and all efficacy outcomes. Subjects will be analyzed according to randomized treatment group.
- Per Protocol (PP) Population – All subjects in the mITT population who received assigned study drug as randomized, completed the Week 4 assessments without any major protocol violations, and have 75-125% compliance. The PP population will be used as an additional population for summaries of efficacy outcomes.
- Safety Population — all subjects in the mITT population who receive at least one dose of study drug. Safety subjects will be summarized according to the treatment they actually received, in case they received a different treatment than assigned at randomization. This population will be used to summarize all safety assessments.
- PK Population — all subjects who receive active study drug and have evaluable PK data based on actual treatment received, protocol compliance, adequate numbers of samples, and successful sample assays.

